9.4.3 Grading of Adverse Events

AE will be graded according to CTCAE v5.0.

9.5 Reporting Adverse Events

9.5.1 All AEs

All events meeting the criteria for AE that occur after the initial dose of FWD1802 during treatment, or within 30 days of the last dose of FWD1802 (including all deaths) must be reported to the Sponsor regardless of cause or assessed relationship to therapy. SAEs will be collected from the time of signed ICF, throughout the entire study, till the follow-up period. SAEs occurring at any time, even after the reporting timeline, must also be reported immediately if suspected to be associated with the study drug.

- The Investigator should instruct the subject to be truthful about changes following the administration. Inducted questions should be avoided;
- Closely monitor AEs or unexpected toxicities (including symptoms, signs, and laboratory tests), analyse reasons and follow-up;
- For AE report, include/attach detailed descriptions about symptoms, severity, time, duration, measurement, the association with study drug, etc. Record should be signed and dated by the Investigator;
- All AEs should be followed-up until resolve, stable or loss of follow-up.

9.5.1.1 SAE

Unless stated by the protocol or other profiles (i.e. investigator's brochure), SAE should be reported to the Sponsor or sponsor assigned safety representative within 24 h of knowledge. The written report should include/attach detailed descriptions including copies of hospital case reports, autopsy reports (if any), and other documents when requested and applicable to the SAE Report. If these items are not immediately available, they are to be provided as soon as possible as a follow-up to the initial SAE Report. For all fatal or life-threatening SAEs contact the Sponsor immediately (as listed on title page of the protocol) and then fax or email the initial report as soon as possible.

Follow-up will be conducted by the Sponsor or sponsor assigned safety representatives and as needed with investigational site personnel to obtain any additional information needed to complete the reporting of the event.

9.5.1.2 Suspected Unexpected Serious Adverse Reaction (SUSAR)

Unexpected adverse event or suspected adverse reaction refers to an event or reaction that is not listed in the investigator's brochure or is not listed at the specificity or severity that has been observed; or, if an investigator's brochure is not required or available, is not consistent with the risk information described in the general investigational plan or elsewhere in the current IND application.

Initial reporting: IND application sponsor must report any suspected adverse reaction or adverse reaction to study treatment that is both serious and unexpected.

SUSAR must be reported to FDA as soon as possible but no later than within 15 calendar days following the sponsor's initial receipt of the information.

Unexpected fatal or life-threatening suspected adverse reactions represent especially important safety information and must be reported to FDA as soon as possible but no later than 7 calendar days following the sponsor's initial receipt of the information.

Follow-up reporting: Any relevant additional information obtained by the sponsor that pertains to a previously submitted IND safety report must be submitted as a Follow-up IND Safety Report. Such report should be submitted without delay, as soon as the information is available but no later than 15 calendar days after the sponsor receives the information.

9.5.2 Follow-Up of AE/SAE

After the initial AE/SAE report, the investigator is required to proactively follow each subject and provide further information to Sponsor on the subject's condition.

AEs that are ongoing with a toxicity of Grade 3 or 4, or have a relationship to investigational drug that is suspected, will be queried for resolution at study conclusion and until resolved or stable and not clinically significant. All SAE's will be followed until they completely resolve, or are otherwise stable. Subjects who discontinue the study due to disease progression should also be followed until adverse event resolves to grade 0-1 or is stable. Once resolved/stabilized, the appropriate AE CRF page(s) or SAE form(s) will be updated. The investigator will ensure that follow-up includes any supplemental investigations as may be indicated to elucidate the nature and/or causality of the AE or SAE. This may include additional laboratory tests or investigations, histopathological examinations, or consultation with other health care professionals.

As reasonably requested by the Sponsor, the investigator will perform or arrange for the conduct of supplemental measurements and/or evaluations to elucidate as fully as possible the nature and/or causality of the AE or SAE. If a subject dies during participation in the study or during a recognized follow-up period, Sponsor will be provided with a copy of any post-mortem findings, including histopathology, if possible.

9.5.3 Post-Study Reporting Requirements

Although such information may not be routinely sought or collected by Sponsor, SAEs that occur after the subject has completed the clinical study may be reported. Such cases will be evaluated for expedited reporting.

9.5.4 Pregnancy

The risks of treatment with FWD1802 during pregnancy have not been evaluated. To ensure participant's safety, each pregnancy in a subject on drug must be reported to the sponsor within 24 h of learning of its occurrence. The pregnancy should be followed up to determine outcome, including spontaneous or voluntary termination, details of the birth, and presence or absence of any birth defects, congenital abnormalities, or maternal and/or newborn complications. Pregnancy and follow-up will be documented, and should include

an assessment of the possible relationship to the IND drug of any pregnancy outcome. Pregnant women who are abortive or need induction of labor should be reported as an SAE.

Pregnancy outcomes must also be collected for the female partners of any males who takes study treatment in the trial, pending consent from the mother.

10 Statistics

A Statistical Analysis Plan (SAP) will be written prior to database lock. The SAP will detail the planned statistical analysis methods to be conducted. A summary of the proposed statistical analysis plan to be conducted is provided in the following sections.

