8. Eastern Cooperative Oncology Group (ECOG) performance status of 0 or 1.
9. At least one measurable lesion according to RECISTv1.1 criteria.
10. Life expectancy ≥ 12 weeks.
11. Adequate organ and bone marrow function (no use of hematopoietic stimulating factor, no blood transfusion or human albumin within 7 days prior to screening):
- Blood routine: Absolute neutrophil count (ANC) $\geq 1.5 \times 10^9/L$; Platelet count (PLT) $\geq 100 \times 10^9/L$; Hemoglobin (HGB) ≥ 90 g/L;
 - Liver function: Serum Total bilirubin (TBIL) ≤ 1.5 Upper limit of normal value (ULN); Alanine aminotransferase (ALT) and Aspartate transferase (AST) $\leq 3 \times ULN$ in subjects without liver metastasis; ALT or AST $\leq 5 \times ULN$ with liver metastasis;
 - Renal function: Serum creatinine $\leq 1.5 \times ULN$ or estimated creatinine clearance (CLcr) ≥ 60 mL/min as calculated using Cockcroft-Gault formula;
 - Coagulation function: Activated Partial thromboplastin Time (APTT) and international normalized ratio (INR) $\leq 1.5 \times ULN$ (or within target range if on anticoagulation therapy);
 - Cardiac function: Echocardiography (ECHO) shows left ventricular ejection fraction (LVEF) $> 50\%$.
12. Women of childbearing potential must have a negative serum pregnancy test within 7 days prior to the first dose. Female patients of childbearing potential must agree to use effective methods of contraception from the time of signature of informed consent, throughout the study and for 6 months after the last dose of the investigational product, like double barrier methods, condoms, oral or injectable contraceptives, intrauterine devices, etc. All female subjects will be considered to be of childbearing potential

unless they are postmenopausal, postmenopausal, or sterilized (hysterectomy, tubal resection).

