7.4.3.3 Long term follow-up (LTFU)

LTFU is survival follow up. After completion of the treatment and safety follow-up period, all the subjects will be followed for survival status. Subjects will be contacted by phone or in person every 12 weeks \pm 7 days after discontinuation to assess survival status until subject death or study termination. Survival and subsequent antitumor therapy will be collected during these calls/interviews.

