8.1.2 Contraception Requirements for Female Subjects of Childbearing Potential

Complete abstinence from intercourse of reproductive potential is an acceptable method of contraception only when it is in line with the subject's preferred and usual lifestyle.

Sexually active female subjects of childbearing potential must agree to use at least 1 highly effective contraception and 1 additional method at least 1 month prior to initiation of the study, during the study, and for 6 months after the last administration of the study drug. Female subjects must also refrain from egg donation and in vitro fertilization during the study and until at least 30 days after the last of study drug.

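### Section 9.5.4 requires pregnancy reporting only for subjects on drug, although contraception is required for 6 months after the last dose, so a pregnancy conceived in those months need not be reported

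*Protocol*

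**What the plan says.** - **Reporting rule (Protocol 9.5.4):** "each pregnancy in a subject on drug must be reported to the sponsor", with a limit of 24 h from when it becomes known. The section then asks for follow-up to outcome and an assessment of the possible relationship to the drug. It states no period after the last dose.
- **Contraception (8.1.2):** sexually active women of childbearing potential must use it from before the study, "during the study, and for 6 months after the last administration of the study drug". Inclusion criterion 12 in Section 5.2 (numbered 11 in the synopsis) agrees: "throughout the study and for 6 months after the last dose of the investigational product".
- **Adverse events (9.5.1):** events during treatment "or within 30 days of the last dose of FWD1802 (including all deaths) must be reported to the Sponsor".
- **Late serious adverse events (9.5.1):** "SAEs occurring at any time, even after the reporting timeline, must also be reported immediately if suspected to be associated with the study drug".
- **Long-term follow-up (7.4.3.3):** "Survival and subsequent antitumor therapy will be collected during these calls/interviews". Pregnancy is not among the items.

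**The concern.** The protocol asks women of childbearing potential to avoid pregnancy for 6 months after dosing ends, but the duty to report a pregnancy is tied to being on drug. A pregnancy conceived two or three months after the last dose lies inside the protocol's own contraception period and outside its reporting rule.

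This matters because Section 9.5.4 itself says that the risks in pregnancy have not been evaluated, and Section 1.2.3 reports adverse ovarian and uterine findings in rats and reproductive-tract findings in dogs. The section wants each pregnancy followed to its outcome and assessed for a relationship to the drug. That aim fails for any pregnancy that the rule does not reach. If post-treatment pregnancies come to the sponsor only when something has gone wrong, there is no count of exposed pregnancies to set the bad outcomes against.

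**Working it through.** The plan gives no figure to reproduce. The check compares periods, taking 6 months as about 183 days.

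**Step 1. Days covered by the pregnancy rule after the last dose.**
- As worded in 9.5.4 (on drug only): 0 of about 183 days.
- With the 30-day adverse event window of 9.4.1 and 9.5.1 read in: 30 days covered, 183 − 30 = 153 uncovered, and 153 / 183 ≈ 84%. This reading is generous, because neither section names pregnancy as an adverse event.

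**Step 2. Does another rule close the gap?**

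| Route | Section | What it catches after the last dose |
|---|---|---|
| Adverse event reporting | 9.4.1, 9.5.1 | Events up to day 30 |
| Safety follow-up visit | 7.4.3.2 | One contact at 28 ± 7 days |
| Long-term follow-up | 7.4.3.3 | Survival and later anticancer treatment; no pregnancy item |
| Abortion or induced labour as a serious event | 9.5.4 | Those outcomes only |
| Birth defect as a serious event | 9.1.2 | That outcome only |
| Late serious events | 9.5.1 | No time limit, but only if the drug is suspected |
| Post-study serious events | 9.5.3 | Reporting optional |

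No row requires a continuing pregnancy, or one that ends in a normal birth, to be reported if it was conceived after the last dose.

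**Step 3. Would the existing long-term contacts reach the end of the period?** The protocol gives two clocks.
- Section 7.4.3.3 counts every 12 weeks (84 days) from discontinuation: days 84, 168 and 252. The last contact inside 183 days is day 168, which leaves 183 − 168 = 15 days after it.
- Note 4 of Tables 1 to 3 counts from completion of safety follow-up. With that visit at its nominal day 28, contacts fall on 28 + 84 = day 112 and 112 + 84 = day 196. The last contact inside 183 days is day 112, which leaves 183 − 112 = 71 days after it. Note 4 also writes the tolerance as ±7 weeks, where 7.4.3.3 has ±7 days.

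On either clock, a question put only at contacts inside the 6 months would miss conceptions late in the period. The first contact after the period is day 252 or day 196 respectively.

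**The case against.** **Bad outcomes still have a route in.** This stands. Birth defects, abortions and induced labour count as serious adverse events, and suspected drug-related serious events are reportable at any time. Section 9.5.1 also says that serious events are collected through the study until the follow-up period, and it is unclear whether that includes long-term follow-up. So it would be wrong to say that post-treatment pregnancies go unreported. The supportable statement is that reporting is not required. Even on the widest reading, these routes catch serious outcomes, not pregnancies.

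**The protocol never calls the 6 months a period of fetal risk.** This also stands. The 6 months is a contraception requirement, and Section 8.1.2 ends the restriction on egg donation and in vitro fertilisation at 30 days, so the protocol does not apply 6 months throughout. The mismatch between the reporting rule and the contraception rule does not depend on that label.

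**Two stronger readings are not supported.**
- A reader might infer that reporting of partner pregnancies is cut short as well. The sentence in 9.5.4 on partners of male participants has neither an on-drug limit nor an end date, so it is open-ended.
- A reader might infer that ovarian suppression stops with the drug, so that conception becomes possible just when reporting ends. Criterion 5 requires the LHRH agonist during the treatment period, but it does not say that suppression stops afterwards, and contraception is still required.

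**Few events are likely.** Entry requires postmenopausal status or LHRH agonist treatment. The protocol gives no expected number of premenopausal patients, so a count cannot be derived. This limits the weight of the point but does not remove the inconsistency.

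**Conclusion.** The point holds as an inconsistency between a stated reporting rule and a stated contraception period. Followed as written, the protocol does not require a pregnancy conceived within 6 months after the last dose to be reported or followed to outcome. The rule covers 0 of about 183 days as worded, and about 30 of 183 if the adverse event window is read in.

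This rests on two assumptions: that being on drug means during dosing, and that 6 months is about 183 days. No study endpoint or dose decision is affected. The point is still worth correcting because it concerns safety information in a first-in-human study and the correction is cheap.

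**What to change.** 1. Reconcile 9.5.4 with 8.1.2 and inclusion criterion 12. Replace the on-drug condition with a reporting period that runs from the first dose to the end of the post-treatment contraception period the protocol already states. This leaves the contraception requirement itself unchanged.
2. If pregnancy status is to be asked in long-term follow-up, for patients of childbearing potential, use the contacts already planned up to and including the first one after that period ends.
3. Reconcile the two long-term follow-up clocks (7.4.3.3, from discontinuation; note 4 of Tables 1 to 3, from safety follow-up) and their tolerances, so that it is clear which contact that is.

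The cost is protocol and CRF wording and, if item 2 is adopted, one question at two contacts (safety follow-up clock) or three (discontinuation clock). No new visit, test or staff is needed.

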10.1 Sample Size Estimate

The sample size estimate of a total of 99 subjects in this trial is based on the enrollment of all parts of the study. This number is considered adequate to determine the safety, tolerability, PK, PD and preliminary efficacy in patients with ER+/HER2- unresectable locally advanced or metastatic breast cancer. The study is summarized below.

Table 13 Sample Size Estimate for the Study

Design	Name of Study	Number of Subjects	Groups
open-label, single arm	Part A: Dose Escalation	27 subjects	5 cohorts (1~6 subjects for each dose level)
open-label, single arm	Part B: Dose Escalation	12 patients	no more than 2 dose levels
open-label, single arm	Part C: Dose Expansion	60 subjects in total	no more than 2 dose cohorts, with 30 patients at the most in one dose cohort

10.2 Analysis Sets

10.2.1 Full Analysis Set (FAS)

All patients who received at least 1 dose of FWD1802.

10.2.2 Safety Analysis Set (SS)

All enrolled subjects who have received the investigational product at least once and have at least 1 valid safety assessment data. They will be used for listings and summaries of safety analysis.

10.2.3 Pharmacokinetic Concentration Set (PKCS)

All enrolled subjects who have received the investigational product at least once and have at least 1 valid concentration data of FWD1802. They will be used for listings and summaries of PK concentrations.

10.2.4 Pharmacokinetic Parameter Set (PKPS)

All enrolled subjects who have received the investigational product at least once and have at least 1 valid PK parameter data of FWD1802. They will be used for listings and summaries of PK parameters.

10.2.5 Pharmacodynamics Analysis Set (PDS)

All enrolled subjects who have received the investigational product at least once and have at least 1 valid (non-baseline) PD data.

10.2.6 Efficacy Analysis Set (EAS)

All enrolled subjects who have used the investigational product and have at least one efficacy observation value.

Upon completion of the dose expansion study, an integrated dose response and exposure-response analyses for the recommended phase 2 dose (RP2D) will be determined.

10.2.7 Interim Analysis

No formal interim analysis is planned for this study. But prior to the dose-expansion part, the investigator, sponsor and medical monitor will review the safety and PK data accumulated in dose-escalation part, and make the decision.

10.3 Data Handling Conventions

Missing data can have an impact on the interpretation of the study data. In general, values for missing data will not be imputed.

Where appropriate, safety data for subjects that do not complete the study will be included in summary statistics. For example, if a subject receive study drug, the subject will be included in a summary of adverse events according to the treatment received; otherwise, if the subject is not dosed then they will be excluded from the summary. If safety laboratory results for a subject are missing for any reason at a time point, the subject will be excluded from the calculation of summary statistics for that time point. If the subject is missing a pre-dose value, then the subject will be excluded from the calculation of summary statistics for the pre-dose value and the change from pre-dose values.

Values for missing safety laboratory data will not be imputed; however, a missing baseline result may be replaced with a screening result, if available. If no pre-study laboratory value is available, the baseline value will be assumed to be normal for the summary of graded laboratory abnormalities.

10.4 Demographic Data and Baseline Characteristics

Demographic and baseline measurements will be summarized using standard descriptive methods, including age, gender, race, weight, past medical and surgical history, vital signs, concomitant medications, and clinical laboratory parameters.

10.5 Safety Analysis

Incidence and severity of adverse events according to the NCI-CTCAE (V 5.0) will be summarized and displayed in number/percentage. The exposure extent to the study drug will be displayed.

10.5.1 Adverse Events

Clinical and laboratory adverse events will be coded using the Medical Dictionary for Regulatory Activities (MedDRA). System Organ Class (SOC), Preferred Terminology (PT), will be attached to the clinical database. See Section 9 for the definition and the severity of AE.

Events will be summarized on the basis of the date of onset for the event. A treatment-emergent adverse event (TEAE) will be defined as following:

- Any AEs with an onset date on or after the study drug start date and no later than 30 days after permanent discontinuation of study drug.
- Any AEs leading to premature discontinuation of study drug.

Summaries (number and percentage of subjects) of TEAEs by SOC and PT will be provided. TEAEs will also be summarized by relationship to study drug and severity. In addition, TEAEs leading to premature discontinuation of study drug and study will be summarized and listed.

All AEs collected during the course of the study will be presented in data listing with a field for treatment-emergent event (yes/no).

10.5.2 Laboratory Evaluations

Selected laboratory data will be summarized (n, mean, SD, median, Q1, Q3, minimum and maximum) by treatment cohorts and time along with the corresponding change from baseline values.

10.5.3 Other Safety Evaluations

The results of scheduled assessments of DLTs, pregnancy tests, physical examination, ECGs, vital signs laboratory tests will be listed for each subject and summarized by dose level and scheduled time point using appropriate descriptive and graphic statistics. The change from baseline data will also be listed.

10.5.4 Pharmacokinetic Analysis

A descriptive analysis of the plasma concentration and derived PK parameters of FWD1802 and its metabolite (if possible) will be conducted by dose level. Plasma concentration patient profiles versus time and mean concentration versus time will be displayed.

10.6 Pharmacodynamics Analysis

Pharmacodynamic analysis will be performed based on PD analysis set. Explore the relationship between exposure or dose of FWD1802 and biomarkers, safety, and clinical efficacy where possible.

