	
of $>38.3^{\circ}\text{C}$ (101°F) or a sustained temperature of $\geq 38^{\circ}\text{C}$ (100°F) for more than one hour;
 
• CTCAE Grade 3 thrombocytopenia ($\geq 25,000/\text{mm}^3$ and $<50,000/\text{mm}^3$) associated with bleeding; 
2. Non-hematological toxicity:
 
• Hy's law, defined as:
◇ AST or ALT > 3 x the upper limit of normal (ULN) AND◇ Total bilirubin > 2 x ULN AND◇ Alkaline phosphatase < 2 x ULN AND◇ No other reason for liver injury• ALT or AST >8x ULN, ALT or AST >5x ULN for more than 2 weeks, ALT or AST >3x ULN and (TBL >2x ULN or INR >1.5)
◇ For patients with hepatic metastases, AST or ALT > 8 x ULN or ALT or AST > 5 x ULN for ≥ 14 days• Grade > 3 non-hematologic toxicity with the exception of the following
◇ Grade 3+ fatigue ≥ 7 days regardless of baseline grade;◇ Grade 3 nausea and vomiting, lasting ≤ 2 days with optimal medical management;◇ Grade 3 diarrhea lasting ≤ 3 days with optimal medical management◇ $\geq 3+$ non-hematologic abnormalities should also include laboratory values that cause symptoms. 
MTD Evaluation period:
 
• Part A: FWD1802 single dose run-in period (C0:D1-D6 intake on D1, then off until D6) and 1st 28-day treatment cycle (C1:D1-D28), total of 34 days;• Part B: the 1st treatment cycle of FWD1802 in combination with palbociclib (C1:D1-D28)
--	---

Duration of treatment	Reiterated treatment cycles of 4 weeks until progression disease based on radiological evaluation, undue drug toxicity, withdrawal of consent or death, whichever occurs first.
PK/PD Sample	Please see Section 7.5.1 PK Samples and Section 7.3.7 18F-FES PET/CT.

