4.2 Methodology

4.2.1 Part A – Dose Escalation of FWD1802 as a Monotherapy

Part A study will be conducted in subjects diagnosed with ER+/HER2- unresectable locally advanced or metastatic breast cancer, to evaluate the safety and tolerability, PK, PD and preliminary anti-tumor activity of FWD1802 Tablet, and to determine RDEs. A maximum of 27 subjects will be enrolled. They will be sequentially allocated to 5 planned dose cohorts: 25 mg, 75 mg, 150 mg, 300 mg and 450 mg.

Subjects enrolled will be orally administered a single dose of FWD1802 Tablet on Cycle 0 Day 1 (C0D1), followed by a 5-day observation period to evaluate the PK and safety of the drug product. Starting on Cycle 1 Day 1 (C1D1), FWD1802 Tablet will be orally administered continuously once or quaque die (QD) for 28 consecutive days of each cycle. The DLT observation period is set as 34 days after the initial administration (1 cycle) (single-dose period and the first 28-day cycle). The second cycle and subsequent cycles will last for 28 days per cycle. The patients will continue to receive the study treatment until disease progression, death, unacceptable toxicity, withdrawal of informed consent, or other reasons to discontinue study treatment occurs, whichever comes first.

Part A will utilize an accelerated dose escalation design to enroll one patient to dose levels 1, which will be converted to a traditional ‘3+3’ design when a grade 2 or higher toxicity occurs during cycle 1 therapy at these dose levels unless it is clearly related to disease progression or extraneous cause, whichever comes first.

Before starting the next dose level, all subjects (n=1, 3, or 6) at the current dose level must complete the DLT observation period. The Safety Monitoring Committee (SMC) will decide whether the study will proceed to the next dose level. Please refer to Section 4.7 Dose modifications.

Based on the safety data, a higher dose level beyond dose level 5 or an intermediate dose level can be explored as determined by the SMC.

The planned escalation dose levels are shown below:

Table 8. The Planned Dose Escalation Levels of FWD1802 in Phase Ia Study

Groups	Dose (mg) *	Percentage of escalation (%)	Number of subjects
1(Starting dose)	25	/	1~3
2**	75	200%	3~6
3**	150	100%	3~6
4**	300	100%	3~6
5**	450	50%	3~6

**Dose levels will be determined based on the results of lower doses, at the discretion of SMC.

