7.3.6 Echocardiogram

Echocardiogram will be performed during the study and left ventricular ejection fraction (LVEF) was recorded.

7.3.7 ^{18}F -FES PET/CT

The patients underwent both ^{18}F -FES and ^{18}F -FDG PET/CT at screening period and C2D8 to monitor the detect in ER target occupation and inhibition. The detection interval between ^{18}F -FES and ^{18}F -FDG PET/CT was within 7 days.

All of the patients were requested to fast for more than 4 h prior to ^{18}F -FES PET/CT scans to eliminate the excretion of ^{18}F -FES from the hepatobiliary system and the gastrointestinal tract, which might interfere with image interpretation in the pelvic cavity.

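### On its natural reading, section 10.6 runs the exploratory exposure-safety and exposure-efficacy analyses on the PD set, which patients who stop for good in Cycle 1 would normally not enter

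*Protocol*

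**What the plan says.** Section 10.6 of the protocol is a two-sentence paragraph. The first sentence fixes a set and the second lists what is to be examined; together they say of the PD work that it "will be performed based on PD analysis set. Explore the relationship between exposure or dose of FWD1802 and biomarkers, safety, and clinical efficacy". The second sentence carries the qualifier where possible. No other set is named.

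Section 10.2.5 limits the PDS to dosed subjects who "have at least 1 valid (non-baseline) PD data".

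The protocol does not formally define PD data. The synopsis row on PK/PD samples reads "Please see Section 7.5.1 PK Samples and Section 7.3.7 18F-FES PET/CT", so FES-PET is the only PD measure with a schedule. Section 3.4 leaves room for further biomarkers but schedules none.

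Section 7.3.7 places the scans "at screening period and C2D8 to monitor the detect in ER target occupation and inhibition". Tables 1, 2 and 3 put the on-treatment scan in the C2D1 column instead. The end-of-treatment visit (7.4.3.1) lists no scan.

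Section 4.2.1 says of Part A: "The DLT observation period is set as 34 days after the initial administration".

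**The concern.** Two of the three relationships named in 10.6, those with safety and with clinical efficacy, do not need a PD value. Running them on the PDS means that a patient counts only after staying on study long enough to be scanned in Cycle 2. Someone who stops for good in the first four to five weeks because of toxicity, clinical deterioration or death is the person an exposure-safety analysis most needs, and would normally be missing.

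Membership of the set is then a post-baseline outcome linked to the outcome being modelled. The estimated risk at a given dose or exposure is too low. The response rate tends to be too high, because a patient who stops that early will rarely have a recorded response. The results are exploratory, but section 4.5 has the RP2D chosen from the totality of PK, PD, efficacy and safety data, so a distorted exposure-safety picture would be one of its inputs.

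**Working it through.** **Timing of the scan against the DLT window** (day 1 = first dose)

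Inputs: a 6-day run-in (synopsis, MTD evaluation period), 28-day cycles, and a ±3-day window at C2D1 (Table 1).

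- The protocol's own figure reproduces: 6 + 28 = 34 days, so the Part A DLT window ends on day 34.
- Part A: C2D1 = 6 + 28 + 1 = day 35 (32 to 38 with the window). C2D8 = 35 + 7 = day 42.
- Parts B and C (no run-in): C2D1 = 28 + 1 = day 29; C2D8 = day 36.
- Tables 1 and 11 label Cycle 0 as 4 days. On that count the Part A dates move 2 days earlier (window end day 32, C2D1 day 33, C2D8 day 40) and the order is unchanged.
- First scheduled tumour assessment, 8 weeks ± 7 days from C1D1: in Part A, 7 + 56 = day 63 (56 to 70). This is after the scan at either time point.

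A permanent stop in Cycle 1 therefore normally comes before the only scheduled post-baseline PD value. Progression found at the scheduled week-8 assessment does not.

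**Size of the distortion (illustration)**

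Let p be the true DLT rate at a dose level and f the share of DLT patients who never reach the scan. The protocol gives neither, so both are assumptions. If all patients without a DLT are scanned, the rate seen in the PDS is

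p(1 − f) / (1 − pf)

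| True rate p | f = 0 | f = 0.5 | f = 0.75 | f = 1 |
|---|---|---|---|---|
| 10% | 10% | 5.3% | 2.7% | 0% |
| 20% | 20% | 11.1% | 5.9% | 0% |
| 25% | 25% | 14.3% | 7.7% | 0% |
| 1/3 | 33.3% | 20.0% | 11.1% | 0% |

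For example, with p = 1/3 and f = 0.5: (1/6) / (5/6) = 0.20. With f = 0.75: (1/12) / (3/4) = 0.111.

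**Effect on the slope**

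The odds seen in the PDS are p(1 − f) / (1 − p), so the log-odds shift by ln(1 − f): −0.69 at f = 0.5 and −1.39 at f = 0.75. If f is the same at every exposure, only the intercept moves and the slope is unchanged. If f rises with exposure, the slope is flattened as well. The dependable effect is on absolute risk.

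**What is not touched**

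Section 10.2.2 assigns safety listings and summaries to the Safety Set, which needs a dose and a safety assessment but no scan. Section 10.3 includes every dosed subject in the AE summary. Section 10.5.3 summarises DLTs by dose level. Sections 4.4 and 4.5 base escalation and the MTD on DLT counts in each cohort.

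**The case against.** The strongest reply is that the restriction is inferred. The second sentence of 10.6 names no set and is qualified by where possible, section 10 is introduced as a summary of a plan still to be written, and PD data are not formally limited to PET. This stands in part: the defect lies in the natural reading, not in an express rule. But the paragraph does name a set. If that set is not meant for the second sentence, the same sentence of clarification is needed.

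Second, section 10.2.6 announces dose-response and exposure-response analyses for the RP2D without mentioning the PDS. That is correct, and the RP2D does not rest on 10.6 alone. However, 10.2.6 assigns no set explicitly. If its position under the Efficacy Analysis Set is meant to supply one, that set requires an efficacy observation, and the first scheduled on-treatment one is at week 8. Unless a baseline scan counts, early stoppers would be lost there too.

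Third, a DLT need not keep a patient from the scan. Table 9 and section 4.7.3 provide for interruption and restart, and with the ±3-day window a Part A scan could fall as early as day 32. This stands: f may be well below 1, and the column f = 0 shows no distortion.

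Fourth, the loss shares are assumed and the slope may hardly move. Both points stand, and they limit the finding to absolute risk and to an illustration of size.

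A reader might go further and infer that the trial's toxicity analyses as a whole omit early stoppers, or that the MTD is compromised. The documents do not support this: the AE and DLT summaries keep those patients, and the MTD rule counts DLTs directly.

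**Conclusion.** The point holds in limited form. The one set that 10.6 names is unsuitable for two of the three relationships it lists, because membership normally requires staying on study to a Cycle 2 scan. Patients who stop permanently in Cycle 1 for toxicity, clinical or off-schedule progression, or death would normally be left out of the exploratory exposure-safety and exposure-efficacy work.

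Absolute risk by dose or exposure would be understated. Under the assumed loss shares, a true 33% DLT rate would read as anything from 33% (no loss) through 20% (half lost) to 11% (three quarters lost). The exposure slope may be little changed.

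The conclusion assumes that the second sentence of 10.6 inherits the PDS, that FES-PET is the operative PD measure, and that some patients do stop before it. It concerns an exploratory analysis that is one input among several to the RP2D, not the primary safety summaries or the MTD.

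**What to change.** Amend 10.6 as follows:

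- Limit the PDS to the FES-PET and other biomarker analyses.
- Run dose-safety on the Safety Set.
- Run exposure-safety on Safety Set patients with any FWD1802 concentration, using exposure measured before the event. Serial first-dose samples are already planned in 7.5.1 (C0D1 in Part A, C1D1 in Parts B and C).
- Run dose-efficacy and exposure-efficacy on the FAS, restricted to patients with exposure data only where exposure is modelled.

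Also reconcile the on-treatment PET time point between Tables 1 to 3 (C2D1) and section 7.3.7 (C2D8), since it determines who can enter the PDS.

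The cost is a short text change and slightly more analysis work. No new data or visits are needed.
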